HEOR	Health Economics, Outcomes & Reimbursement
IBW	Ideal Body Weight
ICH	International Committee on Harmonization
ID	Identifier
INN	International Non-proprietary Name
ITT	Intent-to-treat
IV	Intravenous

IVRS/IWRS	Interactive voice/web response system
IXRS	Interactive response system (independent of type)
JSRC	Joint Safety Review Committee
kBq	Kilobecquerel
LCL	Lower Confidence Limit
LTFU	Long-Term Follow-Up
LTFUAE	Long-Term Follow-Up Adverse Event
MedDRA	Medical Dictionary for Regulatory Activities
MRI	Magnetic resonance imaging
NCI	National Cancer Institute
NCCN	National Comprehensive Cancer Network
NIS	Non-interventional Study
NIST	National Institute of Standards and Technology
nMiss	Number of missing values
OS	Overall survival
PC	Prostate cancer
mPCWG2	Modified Prostate Cancer Working Group 2
PRO	Patient Reported Outcomes
PSA	Prostate specific antigen
PT	Preferred Term
QoL	Quality of Life
Ra-223	Radium-223 dichloride
rPFS	Radiological progression free survival
SAE	Serious Adverse Event
SAF	Safety
SAP	Statistical Analysis Plan
SD	Standard Deviation
SMQ	Standardized MedDRA Queries
SOC	System Organ Class
SOP	Standard Operating Procedure
SSE	Symptomatic skeletal event
SSE-FS	Symptomatic skeletal event free survival
Std	Standard Deviation
TAS	(Bayer) Therapeutic Area (Oncology) Standards
TBW	Total Body Weight
TEAE	Treatment-Emergent Adverse Event
TTP	Time to progression
uCi	Microcurie
UCL	Upper Confidence Limit
W12	Week 12
W24	Week 24
WHO	World Health Organization
WHO-DD	World Health Organization Drug Dictionary

1. Introduction

Protocol 16507 is a 3-arm, randomized, open-label Phase II study to compare the efficacy and safety of a “standard dose” regimen of radium-223 dichloride with, a “high dose” regimen and an “extended dose” regimen, in subjects with castration-resistant prostate cancer metastatic to bone .

The study's 3 arms are:

- Arm A: 6 doses of 50 kBq/kg (55 kBq/kg after implementation of NIST update) radium-223 dichloride every 4 weeks ("standard" dose regimen)
- Arm B: 6 doses of 80 kBq/kg (88 kBq/kg after implementation of NIST update) radium-223 dichloride every 4 weeks ("high dose" regimen)
- Arm C: 12 doses of 50 kBq/kg (55 kBq/kg after implementation of NIST update) radium-223 dichloride every 4 weeks ("extended dose" regimen)

The study's co-primary endpoints are:

- Symptomatic skeletal event free survival from randomization (SSE-FS1) for the "standard dose" vs. "high dose" comparison (Comparison 1).
- Symptomatic skeletal event free survival from the 6th dose (SSE-FS2) for the "standard dose" vs. "extended dose" comparison (Comparison 2)

Two analyses of efficacy and safety are planned in this study:

- A final analysis to occur after the latest of the following maturation criteria are met:
 - 135 SSE-FS (SSE-FS1) events in subjects included in Comparison 1
 - 75 SSE-FS (SSE-FS2) events following the 6th dose in subjects included in Comparison 2
 - The last subject has been followed for 30 days from last treatment.
- An updated analysis to occur after the last subject has completed the active follow-up period in this study for two years following last dose of Ra-223 dichloride (if after primary endpoint cut-off).

Additional details on the timing of the analyses are described in Section 3.3 below.

This Statistical Analysis Plan (SAP) specifies the analyses and data presentations planned for both the final and the updated analysis.

This SAP was written based on the following documentation:

Document	Date	Version
Protocol	9 August 2013	1.0
Protocol Amendment no. 1	20 November 2013	2.0
Protocol Amendment no. 2	16 August 2015	3.0
Protocol Amendment no. 3	16 May 2017	4.0

2. Study Objectives

Co-primary objectives:

- To evaluate efficacy as measured by SSE-FS of radium-223 dichloride 50 kBq/kg (55 kBq/kg after implementation of NIST update) every 28 days for up to 6 doses

compared to radium-223 dichloride 80 kBq/kg (88 kBq/kg after implementation of NIST update); and

- To evaluate efficacy as measured by SSE-FS of radium-223 dichloride 50 kBq/kg (55 kBq/kg after implementation of NIST update) every 28 days for up to 6 additional doses compared to no further radium-223 dichloride treatment in subjects with CRPC metastatic to the bone who previously received radium-223 dichloride 50 kBq/kg (55 kBq/kg after implementation of NIST update) every 28 days for up to 6 doses, and survived SSE free and are eligible for further radium-223 dichloride treatment.

Symptomatic skeletal events (SSEs) are defined as:

- The use of external beam radiotherapy (EBRT) to relieve skeletal symptoms
- New symptomatic pathological bone fractures (vertebral and non-vertebral)
- Tumor-related orthopedic surgical intervention
- Spinal cord compression

Secondary objectives:

- To evaluate safety and tolerability
- To evaluate overall survival (OS)
- To evaluate pain improvement rate
- To evaluate time to pain progression
- To evaluate time to first SSE
- To evaluate time to radiological progression
- To evaluate radiological progression-free survival (rPFS)

Exploratory objectives:

- To evaluate quantitated whole body technetium-99 bone scan tumor burden area and index, and determine bone tumor response
- To explore the impact of patient body size on the efficacy and safety of radium-223 dichloride
- Time to increase in physical symptoms of disease based on the NCCN FACT-P Symptom Index-17 (NCCN-FACT FPSI-17) physical disease related symptoms (FPSI-DRS-P) subscale score measured up to Week 48 after the start of treatment
- To evaluate laboratory indicators of efficacy, including:
 - PSA response
 - Time to PSA progression
 - ALP response
 - Time to ALP progression

- Percentage change in ALP from baseline
- To evaluate change in analgesic use.

[figure not shown]
3. Study Design

This is a three arm, randomized, open-label Phase II study of radium-223 dichloride 50 kBq/kg (55 kBq/kg after implementation of NIST update) versus 80 kBq/kg (88 kBq/kg after implementation of NIST update) , and versus 50 kBq/kg (55 kBq/kg after implementation of NIST update) in an extended dose schedule in subjects with castration-resistant prostate cancer metastatic to the bone. Approximately 360 subjects will be randomized in this study.

The randomization will be stratified by use of prior chemotherapy (≤ 1 regimen versus > 1 regimen), by total ALP (< 220 U/L versus ≥ 220 U/L), and by average worst pain score (WPS) of the Brief Pain Inventory – Short Form (BPI-SF) (WPS ≤ 4 versus WPS > 4).

A schematic of the study design is presented in [Figure 3–1](#).

Figure 3–1: Study Design Schematic

3.1 Study periods and duration

The study periods will consist of screening/randomization, treatment, active follow-up with clinic visits, active follow-up without clinic visits, and long-term follow-up.

Long-term follow-up:

All study subjects will be eligible for further follow-up either in this study or in a separate long-term follow-up study for up to 7 years.

Transition of all subjects into the separate long-term follow-up study will begin following the later of primary endpoint completion or 2 years after the last radium-223 dichloride treatment is administered to the last treated subject.

Until the transition to the long term follow-up study begins, some subjects may begin long-term follow-up in this study. This study will end when all subjects have transitioned into the long-term follow-up study or discontinued from this study for another reason (e.g., Consent Withdrawn, Lost to Follow up).

Data collected in the separate long-term follow-up study is outside the scope of this SAP.

3.2 Schedule of procedures

See Protocol Table 7-1.

3.3 Planned Analyses

The final analysis of this study will take place after the primary endpoint cut-off is reached.

The primary endpoint cut-off will be reached at the later of

- 135 SSE-FS events in subjects included in Comparison 1, and
- 75 SSE-FS events following the 6th dose in subjects included in Comparison 2, and
- the last subject has been followed for 30 days from last treatment.

3.4 Determination of sample size

The sample size is based on two separate comparisons with no multiple-testing adjustment:

Comparison 1:

H01: $SSE-FS_{\text{high dose}} = SSE-FS_{\text{standard dose}}$, versus

HA1: $SSE-FS_{\text{high dose}} > SSE-FS_{\text{standard dose}}$.

This comparison will consider SSE-FS following randomization. Arm C subjects will be pooled with Arm A for the standard dose group. Refer to pooling algorithm in Section 4.5.2 and Censoring rules in Table 9–1.

Comparison 2:

H02: SSE-FS_{extended dose} = SSE-FS_{Standard dose}, versus

HA2: SSE-FS_{extended dose} > SSE-FS_{Standard dose}.

This comparison will include Arm A and Arm C subjects who received 6 or more doses.

The sample size calculations assume 30 subjects/month enrollment with 7 months ramp-up and a 3% loss to follow-up per month. The accrual period is anticipated to last approximately 16 months. Overall, 360 subjects are expected to be randomized at a 1:1:1 ratio. The primary endpoint cut-off, as defined in Section 3.3, is estimated to be reached in an average of 39.1 months.

- Comparison 1 assumes:
 - Arm A (standard dose) subjects have constant median SSE-FS of 9 months throughout the study
 - Arm C (extended dose) subjects have median SSE-FS of 9 months during the first 24 weeks of the study
 - Arm B (high dose) subjects have constant 50% improvement in SSE-FS (median 13.5, hazard ratio 0.667) .

Simulations indicated an average of 186.61 events would occur for this comparison at primary endpoint cut-off, and a 1-sided log-rank test with 0.10 significance gave approximately 90.5% power to test H01 versus HA1.

- Comparison 2 assumes:
 - Arm A (standard dose) subjects have constant median SSE-FS of 9 months
 - Arm C Extended dose subjects have
 - Median SSE-FS of 9 months for the first 24 weeks
 - A 65% improvement (median 14.85, hazard ratio 0.606) thereafter.

With 240 of 360 subjects randomized to Treatment Arm A and Treatment Arm C, simulations indicated that 44.65% of randomized subjects (107.2 of 240) would have a SSE-FS event or loss to follow-up during the first 24 weeks, leaving an estimated 55.35% (132.8) surviving SSE-free and eligible for inclusion at 24 weeks. An average of 74.91 simulated events occurred for this comparison, and a 1-sided log-rank test with 0.10 significance (0.2 for two-sided test) gave approximately 80.6% power to test H02 versus HA2.

Simulations assume continuous event and censoring times. Last treatment is assumed to occur 44 weeks (10.12 months) after last subject accrued.

Primary endpoint power calculations were based on simulations programmed using SAS version 9.2 and used 10,000 replicates.

The simulations, taking into account the correlated nature of the data supporting the two comparisons in this study design, indicated that the proportion of replicates rejecting at least one null hypothesis was 16.4%, and the proportion of replicates rejecting both was 2.3%.

4. General Statistical Considerations

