4.5 Data Rules

4.5.1 Determining Baseline Values

This study has two distinct baselines for efficacy analyses, the randomization baseline and the Week 24 baseline.

Randomization baseline value for efficacy parameters: is defined as the last non-missing value on or before the date of randomization.

Week 24 baseline: Unless otherwise specified, the ‘Week 24 baseline’ is defined as the date of the 6th injection. This baseline is defined only for those subjects who are eligible for Comparison 2 analyses. That is, subjects who had received at least 6 injections.

Week 24 baseline value for efficacy parameters: Unless otherwise specified, the ‘Week 24 baseline value’ is defined as the last non-missing value on or before the date of the 6th injection.

Ideally, this visit would be the date of the 7th injection for Arm C subjects and expected 7th injection date for Arm A subjects. However, the end of treatment visit (30±7 days from last dose) for Arm A subjects could be missing due to consent withdrawal or happen out of visit window. Hence, there is no comparable visit for Arm A subjects that could be used as the expected 7th injection date.

To account for this and achieve comparability between the two arms, the 6th injection date is used as the reference date for Comparison 2 subjects. It should be noted that this could lead to a somewhat dilution of the treatment effect in Arm C due to an early reference date.

Baseline value for safety parameters: is defined as the last non-missing value on or before the date of first dose.

4.5.2 Pooling cut-off date for Arm C subjects in Comparison 1

For Comparison 1, Arm C subjects are planned to be pooled with Arm A subjects. This pooling will be done such a way that only comparable data from Arm C subject pooled. The following algorithm will be used to identify the cut-off date for pooling:

Arm C: Pooling cut-off date = $7*28 + \text{randomization date}$; for subjects that were randomized but not treated,
= $(7-x)*28 + \text{last dose date}$; for $1 \leq x \leq 6$,
= 7th dose date; for $x \geq 7$,
where x be the number of injections received.

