4.7 Additional Statistical Considerations

4.7.1 Delayed Effect Efficacy Assumptions

Since the comparison between the “standard” and “extended” regimens involves identical treatment for the first 6 doses, the following assumptions were made:

- Both regimens have identical efficacy for the first 6 doses, and
- The efficacy would diverge at the time that extended-dosing subjects received their 7th dose.

This feature is consistent with a delayed effect as described in Fine (2007) [1] and Zhang and Quan (2009) [2]. To account for this delayed-effect feature, hazards were modeled using a 2-compartment approach:

- With the standard (Arm A) and high-dose (Arm B) regimens having constant hazards throughout the study, and
- The extended regimen (Arm C) initially having the same hazards as the standard regimen (Arm A) but having a fixed change point at Week 24, approximately the point at which the 7th dose would begin, with constant, reduced hazards thereafter.

A sensitivity analysis using two-compartment Cox model will be performed by taking into account of this delayed-effect feature for Comparison 2. The details are specified in Section 6.2.1.

5. Analysis Sets

- **Intent-to-treat (ITT):** All randomized subjects. The ITT population will be used in the analysis of efficacy endpoints for Comparison 1. Subjects will be included in ITT analyses according to the treatment to which they were randomized as based on IXRS. The randomization baseline will be used in the ITT analyses.
- **Week 24(W24):** All ITT subjects in Arm A (standard dose) and Arm C (extended dosing) treated with radium-223 dichloride and eligible for further treatment at W24 (i.e., 7th injection). Week 24 applies to subjects who received the 6th injection without any dose delays. As dose delays are allowed per protocol, 6th injection can occur after Week 24 for subjects who had dose delays. Hence, this population is defined based on the number of injections not based on the timing. The W24 dataset

will be used for the analysis of efficacy endpoints related to Comparison 2 and associated evaluations. Subjects will be included in W24 analyses according to the treatment to which they were randomized.

- **Safety (SAF):** All subjects who have received at least one study drug administration. This safety population will be used in the analyses of all safety endpoints. Subjects will be included in the analyses according to the treatment they received.

6. Statistical Methodology

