SSE-FS will also be summarized using Kaplan-Meier [5] estimates. Kaplan-Meier [5] curves will be generated, and median survival time together with the 25th and 75th percentiles and associated Brookmeyer-Crowley [6] 80% and 95% CIs will be presented separately for the two comparisons. Kaplan-Meier plots will be presented for the time from randomization for both Comparison 1 and 2. Additionally, similar descriptive summaries will be created for Week 24 population using the randomization baseline.

For each comparison, the contribution of each component of the SSE will be evaluated. Descriptive statistics will be presented.

A Kaplan-Meier [5] curves will be generated for each BMI category (< 18.5 , $\geq 18.5 - < 30$), and ≥ 30) by treatment group within the 2 comparisons. The effect of low baseline BMI status on efficacy will be addressed by including baseline BMI category as a binary covariate (low versus normal/high) in a stratified Cox proportional hazards model.

A 2-compartment Cox model will be fitted as a sensitivity analysis to explore differences between arms A and C for the two time periods before and after the 6th dose, with period as a time-varying covariate. Hazard ratio (and CIs) will be reported for each time period and treatment arm.

Supportive analysis for SSE-FS will be performed for each comparison using a non-stratified log-rank test. The treatment effect (hazard ratio) will be estimated using an unstratified Cox model.

The comparison 2 for SSE-FS will be also performed using randomization baseline as supportive analysis.

As an exploratory analysis, stratified Cox proportional hazards regression models may be fitted for each comparison including other applicable baseline covariates considered to be of prognostic importance. Time-dependent covariates that may be investigated individually in the model include: non-study systemic anti-cancer therapy, increase in analgesics use, radiological progression, pain progression, and pain improvement.

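### Comparison 2's stated 80.6% power and 39.1-month cut-off assume a Week 24 start, but the SAP starts the clock and the 75-event count at the 6th dose; with a W24 set of at least six injections, power is about 71–72%

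*SAP*

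**What the plan says.** **Planning (SAP Section 3.4).** The control assumption is that "Arm A (standard dose) subjects have constant median SSE-FS of 9 months". Arm C has the same hazard for 24 weeks and a hazard ratio of 0.606 afterwards. Of 240 subjects in Arms A and C, 44.65% are expected to have an event or be lost by Week 24, leaving 132.8 for Comparison 2. These produce 74.91 events, and "a 1-sided log-rank test with 0.10 significance (0.2 for two-sided test) gave approximately 80.6% power to test H02 versus HA2". Cut-off is expected at 39.1 months. Section 4.7.1 gives the basis: "The efficacy would diverge at the time that extended-dosing subjects received their 7th dose", at about Week 24.

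**Analysis.** Section 3.3 sets the trigger as "75 SSE-FS events following the 6th dose in subjects included in Comparison 2". Section 4.5.1 says that "the 6th injection date is used as the reference date for Comparison 2 subjects" and accepts that this early date may dilute the Arm C effect. Section 6.2.1 and Table 9–2 start SSE-FS2 on the 6th dose date. The two-compartment Cox sensitivity model is fitted "for the two time periods before and after the 6th dose, with period as a time-varying covariate".

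**Population.** Section 5 describes the W24 set as subjects "eligible for further treatment at W24 (i.e., 7th injection"), then says that the set is defined by number of injections. Sections 3.4 and 4.5.1 use six or more doses. The objective in Section 2 speaks of subjects who survived SSE-free and are eligible for further treatment.

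**The concern.** The power figure and the analysis use different time origins. By the SAP's own assumption the arms are identical until the 7th dose, so an endpoint that starts at the 6th dose opens with four weeks of hazard ratio 1. Events in those weeks pull the estimated effect towards no difference. They also count towards the 75, so the trigger is reached with fewer informative events and earlier than planned. If so, a truly effective extended regimen is more likely to be missed than Section 3.4 implies, and the expected cut-off is wrong as well.

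Section 3.4 also has a minor inconsistency. It gives 16.4% for rejecting at least one null hypothesis and 2.3% for rejecting both, and these do not quite fit two tests of size 10%.

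**Working it through.** **1. When is the 6th dose?** Dosing is 4-weekly and Section 3.4 puts the last (12th) dose at Week 44. The 7th dose is then at Week 24 and the 6th at Week 20. The same section equates 44 weeks with 10.12 months, so 24 weeks = 5.52 months and 20 weeks = 4.60 months.

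**2. Which origin was simulated?** Attrition = 1 − exp[−(ln2/9 + 0.03) × t], with ln2/9 = 0.0770 per month for events and 0.03 for loss.
- t = 5.52: 1 − exp(−0.591) = 44.6%, leaving 132.9 of 240. The SAP states 44.65% and 132.8.
- t = 4.60: 1 − exp(−0.492) = 38.9%, leaving 146.7.

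Only a Week 24 origin matches.

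**3. The stated power.** Schoenfeld approximation, one-sided 0.10, equal allocation: Φ(√74.91/2 × |ln 0.606| − 1.2816) = Φ(2.168 − 1.282) = 81.2%. The Freedman version gives 80.0%. The stated 80.6% is sound for a Week 24 start.

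**4. Full-design simulation.** Inputs from Section 3.4: 360 subjects at 1:1:1, 30 per month after a 7-month ramp-up (taken as linear), 3% monthly loss, the hazards above with the Arm C change at Week 24, and Arm B hazard ratio 0.667. Cut-off is the latest of 135 events, 75 events, and last dose plus 30 days. The test is an unstratified log-rank at one-sided 0.10. Ranges are over repeated runs, mostly of 10,000 replicates (Monte Carlo standard error about 0.45 points near 72%).

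| Comparison 2 origin and stopping | Events (of which before 7th dose) | Cut-off, months | Power |
|---|---|---|---|
| SAP as stated | 74.91 | 39.1 | 80.6% |
| Week 24; 75 events | 74.7 (0) | 38.8–39.5 | 79.5–81.4% |
| 6th dose; 75 events from 6th dose | 75.2 (9.9) | 30.7–31.0 | 71.3–72.1% |
| 6th dose; 75 events after Week 24 (about 85 in all) | about 85 (9.9) | about 39.1 | 76.0–76.4% |
| 6th dose; fixed calendar cut-off | 87–88 (9.9) | 39.1 | 77.5–78.5% |
| 6th-dose clock; W24 requires SSE-free at 7th dose | none before 7th dose | – | 80.3–80.7% |

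A shorter run of 4,000 replicates gave 70.3% for the third row. Modelling loss as a hazard of 0.03 or of −ln(0.97) gave 72.1% either way.

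**5. Hand check of the third row.** With 9.9 of 75.2 events at log hazard ratio 0, the average is (65.3/75.2) × 0.501 = 0.435, a hazard ratio of about 0.65. Power = Φ(√75.2/2 × 0.435 − 1.2816) = Φ(0.604) = 73%, close to the simulation.

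**6. Effect on Comparison 1.** At the earlier cut-off its events fall to about 176 (SAP 186.61) and its power to about 89.7% (SAP 90.5%).

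**7. The 16.4% and 2.3%.** P(at least one) + P(both) equals the sum of the two test sizes, nominally 20%. The stated figures sum to 18.7%. With 10,000 replicates the variance of the count per replicate is 2 × 0.09 + 2 × (0.023 − 0.01) = 0.206, so the standard error is √(0.206/10,000) = 0.45 points. The gap of 1.3 points is about 2.9 standard errors. Re-simulation under no effect in either comparison gave about 17.5–18% for at least one rejection.

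**The case against.** Several points on the other side stand.

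- **80.6% is not a miscalculation.** It reproduces for the design simulated. The fault is that a planning figure was not carried over to the analysis specified.
- **The dilution is disclosed.** Section 4.5.1 states it and gives a reason: Arm A has no comparable visit at the expected 7th injection. Section 4.5.2 shows that a date can be constructed without a visit (last dose plus 28 days after six doses), but that is a censoring date for Arm C. It does not supply an Arm A visit from which to take baseline values such as pain.
- **About 72% is conditional.** A reader might infer that this is simply the trial's true power. It needs the at-least-six-injections reading and stopping at 75 events. At the planned 39.1 months the loss is only about 2–3 points. If W24 requires being SSE-free at the 7th injection, nothing is lost. The dose-count reading prevails in the text, however: Sections 3.4 and 4.5.1 and the end of the Section 5 definition use it, and Table 9–2 has a row for subjects with an SSE before the 6th dose, which an SSE-free requirement would make unnecessary.

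Three stronger inferences are not supported.

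- **Immortal-time bias.** On the SSE-free-at-7th-dose reading, both arms carry the same four event-free weeks. That moves the medians by four weeks but leaves the log-rank test and hazard ratio unchanged. It is also an alternative to the early events, not an addition to them.
- **An invalid test.** The arms are treated alike until the 7th dose and the comparison follows randomised arms, so an early origin costs power and does not raise type I error.
- **16.4% and 2.3% cannot both hold.** Their sum must equal the realised test sizes, which need not be exactly 20%. A gap of 2.9 standard errors is suspicious, not impossible.

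**Conclusion.** The point holds in conditional form. Section 3.4's 80.6%, 74.91 events and 39.1 months describe a Week 24 start, whereas the SAP analyses and counts from the 6th dose. Under the prevailing W24 definition, about 10 of 75 events carry no treatment information, the trigger fires about eight months early, and power is about 71–72%, roughly 9 points below the stated figure.

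This rests on the SAP's planning hazards, no dose delays, every subject SSE-free and in follow-up at Week 20 having had six doses, and an unstratified test. A delay between the 6th and 7th dose, or Arm C subjects stopping after the 6th, would dilute the effect further.

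The 16.4% and 2.3% are a minor matter to recheck. With no multiplicity adjustment planned, a difference of about one point changes no decision.

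**What to change.** 1. Settle on one inclusion rule for the W24 set and use it in Sections 2, 3.4, 4.5.1, 5 and Table 9–2.
2. If the 6th-dose clock and the at-least-six-injections rule stay, re-run the simulation and do one of the following:
   - keep the trigger and restate Comparison 2 power as about 72% and cut-off as about 31 months, updating Comparison 1 events and power to match; or
   - count the 75 trigger events from 28 days after the 6th injection, which returns the cut-off to about 39 months, and restate power as about 76%.

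   Raising the 6th-dose event target is not a practical way back to 80.6%. A target of 95 events gives 79.8% and one of 100 gives 80.7%, but only 69% and 43% of replicates reach them.
3. Add a sensitivity analysis of SSE-FS2 from 6th injection + 28 days in both arms, and split the two-compartment Cox model at that date.
4. Recheck the 16.4% and 2.3% from the sponsor's own simulation output.

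The cost is SAP text and one simulation re-run. The second option in item 2 also delays the cut-off by about eight months relative to the trigger as written. Moving the primary time origin itself would be a larger change to a co-primary endpoint and is not needed to correct the stated figures.
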